We will conduct a two-group randomized controlled trial in primary care clinical settings at two healthcare institutions among 455 Hispanic adults with poorly controlled T2D (hemoglobin A1c \geq 8%). The intervention group will view the 12-minute digital storytelling video. The comparison group will receive usual clinical care. The primary outcome will be glycemic control as measured by hemoglobin A1c 3 months after intervention delivery. Secondary outcomes will include diabetes self-management behaviors, blood pressure, LDL-cholesterol, and body mass index. The impact of concomitant covariates, including sex, age, and socio-economic status, on the sensitivity of the intervention effect will also be explored.

Specific Aim #2: Explore the effect of the digital storytelling intervention on proposed theory-based mediators of change.

Hypothesis 2: Digital storytelling intervention effects on diabetes outcomes will be mediated by social cognitive constructs (self-efficacy, outcome expectancy, social support) and narrative factor constructs (story identification and transportation).

We will assess whether these theoretical factors impact the relationship between intervention effects on diabetes outcomes. A conceptual framework for potential mechanisms will be constructed to describe how digital storytelling may improve these outcomes.

This work is significant because it tests a scalable, low cost intervention targeting vulnerable populations implemented in primary care settings with the opportunity for rapid translation to practice. The innovation comes from utilizing a digital storytelling intervention created through a CBPR process for T2D management among Hispanic adults. By using rigorous and transparent methods, we will establish a disseminable framework for community participation in digital storytelling production for chronic disease management, providing a model that may be applied to other communities and health priorities.

RESEARCH STRATEGY

1. Significance

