This mechanistic complexity of diabetes-related health disparities highlights the difficulty in designing interventions to promote healthy behaviors among Hispanic and immigrant populations^{37,38}. Community-based participatory research (CBPR) is a means to collaboratively investigate healthy living interventions, whereby community members and academics partner in an equitable relationship through all phases of the research.^{39,40} This is an approach to research that is well suited to intervention work that addresses the interplay between health behaviors and the social determinants of health, such that it empowers communities, promotes understanding of culturally pertinent issues, and targets the multi-faceted barriers to health.

Narrative-based (storytelling) interventions incorporate culture-centric health messaging to promote behavior change among vulnerable populations^{13,14}. Storytelling interventions for behavior change use narratives that resonate with target populations either through direct quotes from representative members or through story compositions inspired by culturally embedded informants^{15,41,42}. The ways in which stories elicit behavioral responses among target populations have been conceptualized as *identification* and *transportation*. When narrative is drawn from within populations, identification with the storytellers is an important step for engagement, empowerment, and re-framing social norms of the listener⁴³⁻⁴⁷. Transportation of the listener into the story is likewise important to generate persuasive effects for behavior change^{45,48-51}. For T2D, a group-based storytelling intervention in the United Kingdom demonstrated feasibility and acceptability of this approach among immigrants with T2D in face-to-face (workshop) settings.⁵² Indeed, storytelling interventions may be especially powerful among immigrants when communication barriers limit applicability of existing health education opportunities.⁵³ Furthermore, this approach is promising in populations with a strong oral tradition⁵⁴, including those from Latin America⁵⁵.

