Age, mean (SD)	54.0 (12.7)	56.8 (7.7)	0.53
Female sex, n	6	6	1.00
Baseline hemoglobin A1c, mean % (SD)	10.3 (2.5)	9.9 (2.1)	0.84
Change from baseline to first follow-up A1c, mean(SD)	-1.5 (2.0)	-0.8 (1.8)	0.26

In conclusion, RHCP has spent the last three years developing and evaluating a digital storytelling intervention for T2D self-management among Hispanic adults through a CBPR approach. We have engaged other clinical sites to participate in this project, and we have shown through pilot testing across these institutions that recruitment is feasible, that the storytelling video is acceptable, and that our study team has effective processes for site-specific recruitment and intervention delivery in primary care settings.

Research Design

[figure not shown]
Overview of the general approach. Our approach has followed established methods for behavioral therapy development research^{91,92}. The aim of this research is to evaluate the impact of a digital storytelling intervention

derived through a CBPR approach on T2D outcomes among Hispanic adults with poorly controlled T2D in primary care settings through a randomized clinical trial.

Theoretical approach. The theoretical framework for this work is the application of Social Cognitive Theory (SCT)⁹³ to Narrative Theory.¹³ SCT recognizes the interplay of individual factors, such as self-efficacy to become physically active and social environmental factors like social support, on health behavior. Other key constructs of SCT are outcome expectations or the consequences that result from improved dietary quality (e.g., improved glycemic control). The SCT constructs of self-efficacy, social support, and outcome expectancy have been used successfully to explain self-cares for patients and populations with T2D.⁹⁴ Furthermore, self-efficacy and social support are associated with diabetes self-management behaviors among Hispanic populations⁹⁵⁻⁹⁷. Narrative Theory recognizes the critical role for narrative (stories) as strategies for navigating experience. In this case, the digital narrative will be used for behavior modeling to facilitate observational learning. Narratives incorporate information, communication and persuasion to encourage desired behavior change.¹³ The ways in which the narratives elicit behavioral responses among target populations have been conceptualized as identification with the storytellers⁴³⁻⁴⁷ and transportation of the listener into the story⁴¹⁻⁴⁴ as described above.

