Our clinical trial will assess the potential effect of the proposed intervention on T2D outcomes (physiologic, behavioral, psychological); it will also identify the potential mechanisms of behavior change (i.e., how the intervention works). Figure 1 provides a logic model framework with intervention strategies and outcomes that are consistent with the theoretical framework.

Figure 1. Logic model of intervention strategies and outcomes

Design Overview

This study (Figure 2) will evaluate the intervention through a two-group, parallel randomized controlled trial in primary care clinical settings across two healthcare institutions among 455 Hispanic adults with poorly controlled T2D ($\text{hemoglobin A1c} \geq 8\%$). The intervention group will view the 12-minute digital storytelling intervention that has been previously pilot-tested, in addition to usual clinical care. The comparison group will receive usual clinical care. The primary outcome will be glycemic control as measured by hemoglobin A1c. Secondary outcomes will include diabetes self-management behaviors, blood pressure, LDL-cholesterol, body mass index, and diabetes process measures. We will also measure covariates of treatment effect consistent with our theoretical framework.

Figure 2. Study Design and Intervention Schedule

Month	0	0		0	1	1.5	2	3	3	4	5	6
Activity	Baseline Measures	Randomize	Intervention Group	Digital Storytelling Intervention Usual Clinical Care	Text message	6 week measures	Text message	Text message	3 month measures	Text message	Text message	6 month measures
			Control Group	Usual Clinical Care								

Study Sites

Both clinical sites participated in the pilot testing of the intervention and in refinement of study procedures for the proposed trial. Our letters of support indicate strong investment and commitment to accomplish this study, and study personnel have been identified at both sites:

- Hennepin Healthcare, Minneapolis, MN. Hennepin Healthcare is a large public academic healthcare institution that provides primary care to approximately 90,000 patients in Hennepin County, MN, a large proportion of whom are Hispanic. Members of our study team have worked with HCMC investigators for the past three years on diabetes care for immigrant patients.

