Once eligible patients are identified from institutional registries, the next office appointment for any diabetes-related indication (e.g., chronic disease management provider visit, diabetes educator visit, dietitian visit, diabetes group class, etc.) will be recorded for each patient. These patients will be contacted by telephone by a language-congruent study staff member to introduce them to the study and to assess preliminary interest in participation. Patients will be sequentially recruited at their next office visit until the target accrual is reached. Patients may also be recruited, consented and participate in study activities over the phone.

A language-congruent study staff member will confirm eligibility criteria with the patient and obtain written informed consent in an exam or private room before or immediately after their office appointment. Study staff will then obtain a baseline survey and biometric assessment (see measures) followed by randomization procedures (stratified by gender) and delivery of the digital storytelling intervention (for the intervention group). Each site has developed slightly different protocols for effective recruitment and intervention implementation based on lessons learned from the pilot study. Based on data from our pilot, we expect recruitment and enrollment to occur over a period of no more than 24 months across all sites with the following distribution:

- Hennepin Healthcare: N=240 participants enrolled.
 - Medicine Clinic
 - East Lake Clinic
 - Richfield Clinic
- Mountain Park Health Center: N=215 participants enrolled.

Participant retention will be facilitated in five ways. First, potential participants will confirm the eligibility criteria stating that they expect to receive medical care at the recruitment clinic for at least the next six months (above). Second, appointment cards for both subsequent study visits will be provided to participants after they have completed enrollment. Third, language-congruent study staff will contact patients by phone to remind them about upcoming study visits. Fourth, participants who do not return phone calls from study staff will be sent a letter asking them to call the study coordination to reschedule the appointment. Fifth, participants will receive remuneration at enrollment and at the of the 3 month visit.

Interventions

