Digital storytelling intervention. The digital intervention package, which is 12 minutes long, includes a brief introduction by an RHCP community partner, four stories with transitions, and a short closing educational message re-enforcing the four diabetes self-management behavioral goals (healthful diet, physical activity, medication adherence, glucose self-monitoring). The storytellers include two women and two men; they reflect some of the heterogeneity among Hispanic/Latino subgroups (two Mexican, one Central American, and one South American) in the U.S. After obtaining consent in the clinical setting or over the phone, study staff will deliver the intervention in the exam room, a separate private room or provide patient with a web address to view the video on YouTube from home.

Following the video exposure, study staff will ask these questions to each participant and record their answers: 1) What is your reaction to the video?, 2) What was the main message of the video, and 3) Does the video motivate you to make any changes to the way you manage your diabetes (probe positive responses)? These questions will confirm participant receipt of the intervention, which is an important fidelity construct to ensure that participants received and understood the intervention¹⁰¹.

Participants will be offered a copy of the video as a portable storage device (i.e., “flash drive”) for viewing on a computer, a DVD for viewing on a television, or a web address to watch the video on YouTube. Participants will also be provided access to the storytelling intervention as an application on their mobile phones and/or tablets. In our pilot of the storytelling intervention, all participants cited the use of mobile smart phones. Study staff will offer to assist participants in downloading this application during the baseline visit, and encourage participants to watch the video with family members or friends within their support network.

Figure 3. Still images from the existing digital storytelling intervention

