Secondary analyses. The analyses applied to the primary endpoint will also be applied to each of the secondary endpoints. The subscales from the SDSCA (general diet, diabetes diet, physical activity, diabetes medication use, blood glucose monitoring) and the physical measurements (blood pressure, LDL-cholesterol, BMI) will be compared between groups using t-tests and repeated measures monitoring similar to the primary endpoint. As we have a *single variable* primary endpoint defined, there will be no adjustment for comparison-wise Type I error rate. Additional analyses will be performed to identify potential effect modifiers for the primary and secondary outcomes, i.e., sex, age, socioeconomic position, acculturation, health literacy, and diabetes knowledge.

Aim #2: Explore the effect of the digital storytelling intervention on proposed theory-based mediators of change.

We will examine the correlational structure of the covariates and their impact on the intervention effect size via repeated measures models. We will include procedures suggested by MacKinnon^{129,130} to assess mediation, fitting three general estimating equation models to the data. We will first estimate the intervention effect separately for the dependent variable (with regression adjustment for covariates); that model provides an estimate of the total effect of the intervention. Next, we will estimate the intervention effect for each mediator (with regression adjustment for covariates); that model provides an estimate of the effect of the intervention on the mediator. Finally, we will estimate the mediated intervention effect for the dependent variable by adjusting for the mediator (and covariates); that model provides an estimate of the unmediated (i.e., direct) intervention effect, and the intervention-adjusted effect of the mediator on the dependent variable. These analyses will be done for the primary endpoint and each of the secondary endpoints to identify any mediators of the study results.

Table 3. Study Timeline

Tasks to be completed	Year 1	Year 2	Year 3	Year 4
Recruitment, enrollment, and baseline measures				
Intervention				
Follow-up measurements				
Data analysis				
Dissemination and sustainability plan				

Dissemination and Sustainability Plan

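### For story identification and transportation (2 of the 5 mediators in Hypothesis 2), the three-model procedure cannot give a valid mediated/direct split, because controls see no story during the study

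*Combined protocol and SAP*

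**What the plan says.** Under Specific Aim #2, Hypothesis 2 lists three social cognitive mediators (self-efficacy, outcome expectancy, social support) and two "narrative factor constructs (story identification and transportation").

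The Data analysis plan for Aim #2 fits three models: one for the total effect, one for the effect of arm on the mediator, and one for the outcome adjusted for the mediator. The second step reads "Next, we will estimate the intervention effect for each mediator (with regression adjustment for covariates"). No exception or separate method is given for the two narrative constructs, and the procedure is repeated for the primary and every secondary endpoint.

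Both constructs are described as responses to a story. The Significance section says "Transportation of the listener into the story is likewise important to generate persuasive effects for behavior change". The Theoretical approach says "The ways in which the narratives elicit behavioral responses among target populations have been conceptualized as identification with the storytellers", together with transportation.

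On exposure, the Design Overview says "The comparison group will receive usual clinical care". The Control Condition section offers controls the video package only once the study has finished.

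On measurement:
- Theory-based measures names a 14-item scale for identification and transportation. It gives no arm and no point relative to viewing.
- Table 2 marks the scale at Baseline and at no other visit.
- The Recruitment, Enrollment, Randomization, and Retention section gives the order of procedures: "Study staff will then obtain a baseline survey and biometric assessment (see measures) followed by randomization procedures (stratified by gender"), with the video after that.
- The Measures section also allows theory-based surveys by phone up to two weeks after the clinic appointment, which could fall after viewing.

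**The concern.** A mediator has to be something that assignment can change and that is measurable in both arms. A reaction to a particular story meets neither condition in a participant who has seen no story. The plan nevertheless promises an arm effect on each of these scores and a direct effect adjusted for them.

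What is at stake is the interpretation of exploratory Aim 2. Depending on when the scale is given, the promised result is zero by design, not estimable, or fixed by an arbitrary value. What the data can support is an association among viewers, and that could be reported as mediation unless the plan rules it out. If the scale really is given before viewing, even that association would not be available.

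**Working it through.** The documents give no sample size, power or error rate for the mediation analysis, so there is no stated figure to reproduce. The check is whether the three models are identified.

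**Notation.** A is arm (1 intervention, 0 control), M the narrative score, X a baseline covariate, Y the outcome.
- Model 1: Y on intercept, A, X gives the total effect τ.
- Model 2: M on intercept, A, X gives the arm effect a.
- Model 3: Y on intercept, A, M, X gives the direct effect τ′ and the slope b.
- The mediated effect is a × b.

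The plan uses estimating equations, but the linear predictors have these columns, so the rank argument carries over.

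**Step 1: count.** 3 social cognitive + 2 narrative = 5 mediators, so 2 of 5 are affected.

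**Step 2: scored before randomisation** (Table 2 and the recruitment section read literally). Both arms have scores and the design matrices have full rank: 3 of 3 for model 2 and 4 of 4 for model 3. But randomisation makes the expected value of a zero, so the expected mediated effect is zero whatever b is. In 4,000 simulated trials with 200 per arm, the mean arm effect on the score was -0.001 SD and the mean mediated effect 0.000 SD. There is also no story yet to rate.

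**Step 3: scored after viewing.** Only intervention participants have M, so A = 1 in every usable row and the A column equals the intercept. Model 2 has rank 2 of 3 and model 3 has rank 3 of 4. Neither a nor τ′ is identified. The within-arm model (Y on intercept, M, X) has rank 3 of 3, so the association of score with outcome among viewers can still be estimated.

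**Step 4: a fixed value c assigned to controls.** Replacing c by c + δ changes a to a - δ and leaves b unchanged, because M varies only in the intervention arm. The mediated effect therefore moves by -bδ and the direct effect by +bδ, while τ stays put. Without covariates, mediated = b × (viewer mean - c) and direct = τ - b × (viewer mean - c). Setting c at the viewer mean makes the mediated effect exactly zero. The choice of c decides the split, and the data say nothing about c. The plan names no such value, so no mediated share can be quoted.

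**Step 5: what a within-arm analysis can detect.** The Sample size considerations recruit 225 per group and work with 200 after loss to follow-up. For a partial correlation with one covariate, two-sided 5% and 80% power:

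r = tanh[(1.960 + 0.842) / √(n - 4)]

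- n = 200: tanh(2.802 / √196) = tanh(0.200) = 0.197
- n = 150: tanh(2.802 / √146) = 0.228
- n = 225: tanh(2.802 / √221) = 0.186

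Each further covariate lowers the term under the root by one. With ten covariates and n = 200 it is 187, giving tanh(2.802 / √187) = 0.202, so the figure of about 0.20 is stable.

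**The case against.** The best defence is that the scale is plainly meant for viewers, after the video. Figure 2 places baseline measures, randomisation and the video all at month 0, so a Baseline entry in Table 2 is compatible with scoring after viewing. Rating a story before seeing it makes no sense, so Step 2 may be only a scheduling ambiguity. This is fair, but it leads straight to Step 3, where the stated models cannot be fitted as intended.

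A second defence is that controls, having seen nothing, sit at a natural floor of no identification and no transportation, so a split could be computed. It could, but only under linearity, extrapolation to an unobserved score and no confounding of score and outcome. The plan states neither the floor nor these assumptions.

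Third, the Measures section refers to a Study Tasks Table that is not in the text available. Arm or order may be given there. This limits how firmly one can say they are unstated; it does not change the identification problem.

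A reader might also infer more than the documents support:
- That the timing of the scale is missing altogether. It is not: Table 2 gives the visit. What is absent from the available text is the arm and the order relative to the video.
- That the plan intends to assign controls a score. Nothing in it proposes this.
- That Aim 2 as a whole fails. The other three mediators are scheduled at baseline, 6 weeks, 3 months and 6 months with no restriction by arm, and this problem does not touch them.

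**Conclusion.** The point holds for 2 of the 5 mediators in Hypothesis 2. Under neither natural timing of the scale do the three models yield a valid mediated/direct split for story identification and transportation, and assigning controls a value only moves the decision to whoever picks the value. The conclusion rests on controls not seeing the video during the study, as the Control Condition section states, and on the two constructs being reactions to that story, as the protocol itself describes them.

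The reach is limited. Aim 2 is exploratory. The primary comparison of A1c at 3 months, the secondary between-group comparisons and the sample size are unaffected. It should still be corrected, because this is a stated analysis that cannot deliver what it promises, and the correction is cheap.

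**What to change.** 1. In Theory-based measures and Table 2, state that the scale is completed by intervention participants after their first viewing, in clinic or remotely. The Digital storytelling intervention section already provides the contact: "Following the video exposure, study staff will ask these questions to each participant and record their answers". It lists three open questions there, to which the scale could be added. Because staff may also "provide patient with a web address to view the video on YouTube from home", the wording should cover remote viewers.
2. Restrict the three-model procedure to self-efficacy, outcome expectancy and social support.
3. Analyse identification and transportation within the intervention arm only, as exploratory, non-randomised predictors of 3-month outcomes adjusted for the baseline value, and say that the result will not be reported as mediation.
4. Reword Hypothesis 2 to match.

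The cost is protocol and analysis-plan wording plus one Table 2 entry. If the scale is now given before randomisation, its timing has to move. The scientific price is a narrower Hypothesis 2: the two narrative constructs become correlates of outcome among viewers.

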racial/ethnic minority populations, which showed a similar hemoglobin A1c reduction of 0.31 standard deviations¹²⁸. While these effects sizes are smaller than that of our pilot study, we have picked the more conservative (lower) estimate of effect size to ensure ample sample size. Hence, we can expect an effect likely to be between 0.25 and 0.31 standard deviation for the type of intervention proposed. Required sample sizes for an independent samples t-test to detect these two effect sizes, assuming 80% power, a two-tailed alternative and a 5% Type I error rate, are 252 and 145 patients per group, respectively. With 200 patients per group, we will have 80% power to detect an effect size of 0.28 standard deviations via the independent samples t-test. Accounting for approximately 12% loss to follow-up, we intend to recruit 225 patients in each group, for a total sample size of 450 participants.

Data analysis plan

Aim #1: Evaluate the efficacy of a community-derived digital storytelling intervention among Hispanic adults with poorly controlled T2D.

The primary analysis will be an independent samples t-test between the group average hemoglobin A1c values at 3 months. A two-sided alternative with a 5% type I error rate will be employed.

Supplementary analysis for the primary endpoint. Repeated measures modeling of the individual time point A1c values (including chart abstracted values at approximately 6 months) will allow for a more detailed investigation to the timing of the impact of the intervention by including all time points (including baseline). Profile analysis (Srivastava) will further assess for difference in overall means, time point, and treatment by time interactions. Covariates indicated above including demographics and clinical covariates will be included in the repeated measures and profile analysis models to assess the sensitivity of the primary analysis conditional on these potential concomitant (mediating) influences.

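### Aim 2 models each mediator on its own, so if the social cognitive constructs are correlated and the video moves several of them, it cannot show which one carries the effect on A1c

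*Combined protocol and SAP*

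**What the plan says.** Hypothesis 2 (under Specific Aim #2) expects the effect on diabetes outcomes to be "mediated by social cognitive constructs (self-efficacy, outcome expectancy, social support) and narrative factor constructs (story identification and transportation"). The data analysis plan for Aim #2 gives a three-model procedure using general estimating equations:

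- The first model estimates the whole intervention effect on the outcome, adjusted for covariates.
- For the second, the plan states "we will estimate the intervention effect for each mediator (with regression adjustment for covariates").
- The third estimates the direct effect and the mediator's own effect "by adjusting for the mediator (and covariates"), with the mediator in the singular.

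The set is repeated for the primary and every secondary endpoint "to identify any mediators of the study results". The section also promises a look at how the covariates correlate and how they affect the intervention effect, but carries none of that into the mediation models. It states no test of the indirect effect and no rule for calling a construct a mediator. The documents report no correlation between the constructs and no expected shift in any of them.

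**The concern.** The three social cognitive constructs are reported by the same participants at the same four time points (Table 2), so some correlation is plausible. In an outcome model with one mediator, that mediator's coefficient also picks up the effect of any correlated construct left out. Randomisation protects the estimate of what the video does to each construct. It does not protect the estimate of what each construct does to A1c.

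Aim 2 is meant to show how the video works and to feed a conceptual framework of mechanisms. If several constructs move together, separate models may name all of them as mediators when one does the work, and their mediated shares overlap.

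**Working it through.** **Inputs from the documents.** 200 analysed per group, 1:1, two-sided 5% (Sample size considerations). The plan's own figure reproduces: "With 200 patients per group, we will have 80% power to detect an effect size of 0.28 standard deviations" gives Φ(0.28 × √(200/2) - 1.96) = Φ(0.84) = 80%. That section gives no figure for mediation.

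**Assumed inputs.** Every variable has within-arm SD 1. The video moves the active construct by a₁ = 0.3 SD, and that construct acts on A1c with b₁ = -0.3 SD per SD. A second construct is inert (no effect of its own on A1c), has within-arm correlation r = 0.3 to 0.6 with the active one, and is moved by a₂ = 0, 0.15 or 0.3 SD. A construct is declared a mediator when both of its paths are significant. One time point, least squares, no measurement error.

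**Bias in the single-mediator model.** The inert construct's coefficient on A1c is r × b₁ instead of 0, so its apparent indirect effect is a₂ × r × b₁. At a₂ = 0.3:

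- r = 0.3: 0.3 × 0.3 × (-0.3) = -0.027 SD
- r = 0.6: 0.3 × 0.6 × (-0.3) = -0.054 SD

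The true mediated effect is 0.3 × (-0.3) = -0.09 SD, so the inert construct is credited with 30% to 60% of it.

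**How often it is declared.** The rate is close to the product of two powers.

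- Video to construct: Φ(a₂ × 10 - 1.96), which is 32% at 0.15 SD and 85% at 0.3 SD. At a₂ = 0 it is the 5% error rate.
- Construct to A1c: Φ(0.3r / SE - 1.96), with SE = √((1 - 0.09r²)/400), about 0.05.

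| r | Construct-to-A1c path significant | a₂ = 0 | a₂ = 0.15 | a₂ = 0.3 |
|---|---|---|---|---|
| 0.3 | 44% | 2% | 14% | 37% |
| 0.4 | 68% | 3% | 22% | 58% |
| 0.5 | 86% | 4% | 28% | 73% |
| 0.6 | 96% | 5% | 31% | 81% |

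Simulation of the same cases gives 2-5%, 12-30% and 37-80% across r = 0.3 to 0.6, in agreement. The rate cannot exceed the power of the video-to-construct test.

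**Joint model.** With the constructs entered together, the inert one's coefficient averages 0. Its declaration rate is about 5% × (power of the video-to-construct test), which at a₂ = 0.3 is 5% × 85% = 4%. Simulation gives 4.0-4.6% there and less for smaller shifts.

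**Overlap.** With one active and two inert constructs, all moved by 0.3 SD, the three single-mediator indirect effects sum to 0.09 + 2 × 0.027 = 0.144 SD at r = 0.3 and 0.09 + 2 × 0.054 = 0.198 SD at r = 0.6. The true mediated effect is 0.09 SD.

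**Dependence on the decision rule.** The plan gives none. With a₁ = a₂ = 0.3 and b₁ of size 0.3, a Sobel test declares the inert construct in 18% of trials at r = 0.3 and 52% at r = 0.5, against 36% and 73% when both paths must be significant.

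**Cost in power.** In that setting the joint model detects the true mediator as often as the single model (85% in each at r = 0.3 and 0.5). Over the wider range tried, the largest loss was from 84% to 70%, at b₁ of size 0.2 and r = 0.7.

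**The case against.** **Correlation alone does little.** A reader might infer that any construct correlated with the active one will often be declared a mediator. The numbers do not support that. If the video leaves the inert construct unmoved, the rate is about 5% or below. High rates need a real shift in that construct, and the documents give none: the pilot reports a change in confidence only, with nothing on outcome expectancy or social support. This stands, and the 37-80% range is the upper row of a conditional result. In its favour, Hypothesis 2 itself expects mediation through all three constructs, which requires the video to move all three.

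**The word covariates may already include the other constructs.** The Design Overview speaks loosely of covariates tied to the theoretical framework. But the first Aim #2 model is adjusted for covariates too, and is said to give the whole intervention effect. It could not do so if the other mediators were among them. The supplementary analysis under Aim #1 names demographic and clinical covariates. One mediator at a time is the coherent reading, though a definition would settle it.

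**A joint model is not simply right.** The Theoretical approach section describes self-efficacy and social support as interacting, so one may act through the other. Suppose the video raises support by 0.3 SD and support acts on A1c only through self-efficacy (assumed path 0.5, then -0.3). Support's real mediated effect is 0.3 × 0.5 × (-0.3) = -0.045 SD. The single model recovers it and declares it in 71-73% of trials. The joint model puts it at about 0 and declares it in 4%. This stands, and it rules out replacing or demoting the single-mediator models.

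**The shares need not exceed the whole effect.** A reader might also infer that the mediated shares add to more than the full intervention effect. Here they exceed the true mediated effect (0.09 SD), but at 0.144-0.198 SD they stay below the 0.28 SD the trial is sized to detect.

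**Conclusion.** The point holds in conditional form. As written, the Aim 2 models cannot separate correlated constructs that the video moves together. How often that misleads depends on the correlation, the size of each shift, the strength of the active path and the rule for declaring a mediator. The documents give none of these, so the rates in the table are indicative only.

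Neither kind of model is sufficient alone. Single-mediator models mix correlated constructs, and a joint model can hide an upstream one. Aim 2 is exploratory, so this limits what may be said about mechanism. The A1c comparison at 3 months is untouched.

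**What to change.** In the data analysis plan, Aim #2:

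1. Add, for each outcome, a version of the third model with self-efficacy, outcome expectancy and social support entered together. Report each specific indirect effect and the total indirect effect with bootstrap intervals.
2. Keep the one-at-a-time models and report the two side by side. State that the single models do not separate correlated constructs, and that the joint model gives only the part of each construct's effect not carried through the others, so an upstream mediator can appear inert.
3. Define which variables count as covariates, and state the test or interval used for the indirect effect.

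The cost is a few sentences and a little more analysis. No new data are needed and the primary analysis does not change. Intervals for the specific effects will be somewhat wider when the constructs are highly correlated.
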